Version 6.0	
Revised dose escalation/de-escalation/stopping /continuation rules based on end of Cohort 1 SMG safety review and recommendation 23Mar2023:
 
 Added “Continue to next higher dose group if 3 or more patients show peak ACT <200 sec in Cohort 2” to avoid inadequate treatment in cohort 2. Modified “Stop study drug infusion in an individual patient only temporarily and eliminate conditions if ACT <180.” The specific dosing adjustment guideline provided, therefore study drug infusion can be resumed to ACT at target level. Modified the criteria in Stop the study if: both more than 3/6 ACT >350 sec and more than 2/6 patients experience bleeding events with BARC 3-5. Both ACT as anti-coagulation level biomarker and actual significant bleeding events with BARC 3-5 are needed to justify study to be stopped due to significant risk of bleeding. 
Proposed new dosing regimen for cohort 3 at 0.75 mg/kg + 1.6 mg/kg/h*4h and dose adjustment guideline for cohort 3 dosing regimen per SMG’s recommendation based on the following findings in Cohort 1 and PK/PD modeling results from Phase I study:
 
 MT1002 was safe and well-tolerated in all 6 patients enrolled in the 0.90 mg/kg+1.8mg/kg/h*4h cohort of the study. None of the patients who received MT1002 experienced serious adverse events, major bleeding events or major adverse cardiovascular events. At 0.90 mg/kg+1.8mg/kg/h*4h dose-level, MT1002 achieved targeted ACT level resulting in successful PCI in all 6 patients. 3 patients had one peak ACT >300 after bolus injection at 5 minute, indicated the bolus dosing at 0.9 mg/kg can be reduced. 0.75 mg/kg is recommended by SMG if 0.6 mg/kg shows inadequate anti-coagulate effect. Only 1 patient had one peak ACT >300 at 30 minutes during infusion period, indicated 	16-Apr-2023
-------------	--	-------------

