	
the infusion dose at 1.8 mg/kg/h*4h can be reduced slightly. 1.6 mg/kg/h*4h is recommended by SMG if 1.2 mg/kg/h*4h mg/kg shows inadequate anti-coagulate effect.
 
 Phase I PK /PD modeling results indicate 0.75mg/kg+1.6mg/kg/hr*4h is an effective dose. 
Dose adjustment guideline for cohort 3 dosing regimen is provided to ensure the ultimate dosing regimen can be identified and confirmed for future phase 3 trials.
 
Clarified that patients who are enrolled but do not undergo PCI (e.g., because of PCI contraindication revealed after coronary angiography or due to exclusion criteria) will be evaluated as safety population.
 
Specified a total of up to 18 patients on MT1002 (3 cohorts of 6 patients) will be enrolled in the study based on cohort 2 results.
 
Revised content related to aspirin, or clopidogrel or Ticagrelor or Prasugrel use before and at the time of PCI:
 
All patients will receive either aspirin or loading dose of clopidogrel (600 mg) or Ticagrelor or Prasugrel if not already on maintenance dose need to be either before PCI or otherwise at the time of PCI - deleted “on admission”. The rationale is that the investigators may not have contact of the patient “on admission” so prescribing therapy is difficult.
 
Updated Exclusion Criteria #6 - removed “staged PCI” since there is no specific safety concern and not necessary to exclude patients with staged PCI for this study.
	
--	--	--

PROTOCOL APPROVAL SIGNATURES

Protocol Title: Open-Label, Sequential-Dose Escalation/De-escalation Trial Testing MT1002 in Patients Undergoing PCI Due to Acute Coronary Syndrome with NSTEMI

Protocol Number: MT1002-II-C01

This study will be conducted in compliance with the clinical study protocol (and amendments), International Council for Harmonisation (ICH) guidelines for current Good Clinical Practice (GCP) and applicable regulatory requirements.

Sponsor Signatory

[name], PhD
Chief Medical Officer
Shaanxi Micot Technology Co. Ltd

DocuSigned by:
[name]
Signer Name: [name]
Signing Reason: I approve this document
Signing Time: 4/21/2023 | 2:50:38 PM PDT
72C63413C5FA436FA94579048F85C759

Signature

Date

[name], MBA
Sr. Director, Clinical Operations
Shaanxi Micot Technology Co. Ltd

DocuSigned by:
[name]
Signer Name: [name]
Signing Reason: I approve this document
Signing Time: 4/21/2023 | 2:50:00 PM PDT
D4822022C98C4204A7B8B53630F56686

Signature

Date

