There were no deaths, serious adverse events (SAEs), discontinuations of study drug due to a TEAE or withdrawals due to a TEAE. Of the 13 adverse events (AEs), nervous system disorders, the most commonly reported SOC, were reported by 1 subject in Cohort 3 (headache) and 2 in Cohort 5 (headache and dizziness). Gastrointestinal disorders were reported by 1 subject in Cohort 4 (discolored feces) and 1 in Cohort 5 (mouth hemorrhage). General disorders and administration site conditions were reported by 1 subject in Cohort 3 (injection site bruising and injection site nodule) and 1 in Cohort 5 (injection site hemorrhage). Each treatment-related TEAE was reported by a single subject. All TEAEs were Grade 1 in severity, and all patients recovered.

The results of the study showed that continuous IV infusion for 4 hours was safe and well tolerated in healthy subjects and had significant effect on coagulation function. The MTD in healthy subjects was 1.2 mg/kg + 2.3 mg/kg/h*4h. MT1002 had a fast elimination rate in the human body and was positively correlated with dose.

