4.4 Study Rationale

Therapies for ACS includes antithrombotic therapy and glycoprotein IIb/IIIa receptor antagonists (GPI) as well as anticoagulant therapy. Additional therapeutic measures that may be indicated include thrombolysis and PCI. The goals of pharmacotherapy in PCI are to reduce morbidity and prevent complications. Heparin has been the mainstay of anticoagulation during PCI in patients with angina and ACS for decades. However, the choice of anticoagulation for PCI remains a hotly debated issue. MT1002 is a novel 32-amino acid synthetic peptide aimed to combine molecular functions of both a direct thrombin inhibitor and a platelet glycoprotein IIb/IIIa receptor antagonist, and other characteristics of an ideal parenteral anticoagulant, i.e., to be immediately effective, easily dosed so as not to require frequent monitoring, free of dose adjustment in renally or hepatically impaired patients, and predictably reversible, indicated for use as an antithrombotic and anticoagulant in patients with ACS and in patients undergoing PCI. This study is to investigate the safety, tolerability, and efficacy of MT1002 in patients undergoing PCI due to ACS with NSTEMI.

Three doses of MT1002 (IV loading + continuous IV infusion) will be sequentially tested. The first dose level is 0.90 mg/kg initial loading dose (bolus intravenous injection) + 1.8 mg/kg/h (infusion) for 4 hours. The second dose level will be based on the results from the first cohort (If the dose is escalated, then the second dose level is 1.2 mg/kg initial loading dose (bolus intravenous injection) + 2.3 mg/kg/h (infusion) for 4 hours; if the dose is de-escalated, then the second dose level is 0.6 mg/kg initial loading dose (bolus intravenous injection) + 1.2 mg/kg/h (infusion) for 4 hours). The third dose will be determined based on the results from the first 2 cohorts. The doses of 0.90 mg/kg+ 1.8 mg/kg/h*4h, and 1.2 mg/kg+2.3 mg/kg/h*4h were tested in the Phase 1 healthy volunteer study and were considered to be safe and well tolerated, with the 1.2 mg/kg+2.3 mg/kg/h*4h dose declared the MTD.

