All patients will receive 0.75 mg/kg as an IV bolus dose, followed immediately by 1.6 mg/kg/hr*4h IV for the duration of the PCI. Five minutes after the bolus dose, ACT should be performed and an additional bolus of 0.3 mg/kg IV may be given if needed (i.e., ACT <200 sec).

- Dosing during infusion period

10 minutes after initiation of 1.6 mg/kg/hr IV for the duration of the PCI, or 5 minutes after additional bolus if it is given, additional ACT can be monitored, and IP infusion rate can be adjusted. An incremental 10% additional infusion rate can be titrated up until ACT >200 sec. If ACT >300 sec during that period of time, IP infusion can be stopped for 5 minutes, and/or the rate of infusion can be adjusted until ACT maintains between 200 sec and 300 sec. Duration of IP infusion can be 4 hours +/-30 minutes in order to accommodate potential infusion rate adjustments.

Table 3 Planned Dose Regimen of MT1002 for Injection and Expected ACT and aPTT Values

Sequence	N	MT1002: Initial loading dose and maintenance dose	Expected peak ACT based on Phase 1 results in healthy volunteers	Expected peak aPTT based on Phase 1 results in healthy volunteers	Expected ACT in 5 min after MT1002 start	Expected aPTT in 5 min after MT1002 start	Expected ACT in 30 min after MT1002 start	Expected aPTT in 30 min after MT1002 start
First dose cohort	6	0.90 mg/kg + 1.8 mg/kg/h*4h	234.3±26.1 sec – at 4 hours	74.4±6.2 sec – at 4 hours	209.7±19.2	63±4.8	212.3±29.5	65.6±7.5
Second cohort if dose escalated	6	1.2 mg/kg + 2.3mg/kg/h*4h	253.8±9.6 sec – at 2 hours	83.6±5.4 sec – at 4 hours	234.3±6.9	74.5±7.3	240.3±4.1	78.3±9
Second cohort if dose de-escalated	6	0.60 mg/kg + 1.2 mg/kg/h*4h	221.7±11.1 sec – at 2 hours	65.9±2.5 sec – at 4 hours	194.5±28.6	56.5±7.4	216.2±15.7	60.6±4.4
Third expansion cohort	6-8	0.75 mg/kg + 1.6 mg/kg/h*4h based on results from initial 2 cohorts	220.7 sec at 4 hours	67.7 sec at 4 hours	217.5	66.5	216.5	66.1

Abbreviations: ACT, activated clotting time; aPTT, activated partial thromboplastin time; h, hours; min, minutes; N, number of patients; sec, seconds; Tbd, to be determined.

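### The Cohort 3 titration guideline sets no maximum rate, step base or later-step interval, so it permits an infusion rate above the declared MTD rate of 2.3 mg/kg/h

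*Combined protocol and SAP*

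**What the plan says.** The guideline is in section 8.2 and is repeated in the synopsis. Every Cohort 3 patient starts with a 0.75 mg/kg bolus and 1.6 mg/kg/h. If the 5-minute ACT is low, "an additional bolus of 0.3 mg/kg IV may be given if needed (i.e., ACT <200 sec". The first rate change may come 10 minutes after the infusion starts, "or 5 minutes after additional bolus if it is given, additional ACT can be monitored". After that, "An incremental 10% additional infusion rate can be titrated up until ACT >200 sec". Above 300 sec the infusion may be paused for 5 minutes or its rate adjusted. The infusion may last up to 4.5 hours.

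The other limits are:
- Sections 6.1 and 9.2.3: a patient not at target within 30 minutes of infusion start goes to standard of care. Section 9.2.3 words this as a decision made before PCI.
- Section 6.1, Table 1: temporary stop at ACT above 350 or below 180 sec. The synopsis version has only the upper limit.
- Section 11.6.9 (Overdose): no numeric threshold.

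On the reference dose, section 4.2.2 states "The MTD in healthy subjects was 1.2 mg/kg + 2.3 mg/kg/h*4h", and section 4.4 agrees: "with the 1.2 mg/kg+2.3 mg/kg/h*4h dose declared the MTD". The guideline does not refer to it.

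**The concern.** The titration rule has a stopping condition, an ACT above 200 sec, but no ceiling. A patient who responds weakly on ACT triggers none of the upper ACT limits, so nothing in the text holds that patient at or below the highest infusion rate that the documents show was given to humans. Cohort 3 patients also take aspirin and a P2Y12 inhibitor. MT1002 is itself a glycoprotein IIb/IIIa inhibitor, yet only ACT guides the rate. It is an inference, but a fair one, that raising the rate for a low ACT also raises antiplatelet exposure that the titration does not track.

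There is also a reproducibility issue. The Version 6.0 entry in the summary of changes says the guideline exists "to ensure the ultimate dosing regimen can be identified and confirmed for future phase 3 trials". With the step base and interval undefined, two sites following the text exactly could deliver different rates for the same ACT readings.

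**Working it through.** **Inputs.** Section 8.2: starting rate 1.6 mg/kg/h; step 10%; first step at minute 10; total bolus with top-up 0.75 + 0.30 = 1.05 mg/kg; duration 4 h, at most 4.5 h. Sections 4.2.2 and 4.4: MTD regimen 1.2 mg/kg + 2.3 mg/kg/h for 4 h. The plan gives no maximum rate, so there is no stated figure to reproduce. As a check on the dose formula, 70 kg × (0.15 + 0.3 × 4) = 94.5 mg, which matches the Phase 1 starting dose in section 4.2.2.

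**Rate after k steps, with no interval assumed.** Compounded: 1.6 × 1.1^k. Additive, as 10% of the starting rate: 1.6 + 0.16k.

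| k | Compounded (mg/kg/h) | Additive (mg/kg/h) |
|---|---|---|
| 1 | 1.76 | 1.76 |
| 2 | 1.94 | 1.92 |
| 3 | 2.13 | 2.08 |
| 4 | **2.34** | 2.24 |
| 5 | 2.58 | **2.40** |

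The first rates above 2.3 are in bold: 2.343/2.3 = 1.019 (+1.9%) and 2.40/2.3 = 1.043 (+4.3%). Four additive steps stay below: 2.24/2.3 = 0.974 (−2.6%).

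**Timing against the 30-minute rescue point.** The interval is an assumption, because the plan gives none after the first step.
- Every 10 min (minutes 10, 20): two steps, 1.94 or 1.92. No excess.
- Every 7 min (minutes 10, 17, 24): three steps, 2.13 or 2.08. No excess.
- Every 5 min, the shortest ACT spacing the guideline itself uses (minutes 10, 15, 20, 25): four steps, 2.34 or 2.24. Only the compounded reading passes 2.3, at minute 25. The fifth additive step would fall at minute 30.

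**After 30 minutes.** Section 8.2 sets the 200 to 300 sec goal for the continuous infusion, and no text ends titration at 30 minutes. A patient who reached target in time and then drifts to between 180 and 200 sec may be stepped up again, with no limit on the number of steps. Table 5 schedules no ACT between 0.5 h and 4 h, so this would depend on unscheduled readings.

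**Total dose (secondary, since section 4.2.2 reports that "MT1002 had a fast elimination rate in the human body").** The MTD regimen totals 1.2 + 4 × 2.3 = 10.4 mg/kg. Take the 1.05 mg/kg bolus and 5-minute steps, with the last rate held:
- Compounded, 4 h: 1.05 + (1.6×10 + 1.76×5 + 1.936×5 + 2.1296×5 + 2.3426×215)/60 = 10.20 mg/kg. At 4.5 h: 10.196 + 2.3426×0.5 = 11.37.
- Additive, 4 h: 1.05 + (1.6×10 + 1.76×5 + 1.92×5 + 2.08×5 + 2.24×215)/60 = 9.82 mg/kg. At 4.5 h: 9.823 + 2.24×0.5 = 10.94.

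Both totals are below 10.4 at 4 h and above it only at the 4.5 h maximum.

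**Likelihood.** In Cohort 1, at 0.90 mg/kg + 1.8 mg/kg/h, "MT1002 achieved targeted ACT level resulting in successful PCI in all 6 patients", and three of the six peaked above 300 sec at 5 minutes. A Cohort 3 patient given the top-up and two steps (1.05 mg/kg; 1.92 to 1.94 mg/kg/h) is already above that regimen on both components. Table 3 expects 217.5 sec at 5 minutes and 216.5 sec at 30 minutes in Cohort 3 with no adjustment.

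**The case against.** The case for leaving the text alone has several sound parts.

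- **The window is narrow.** Before rescue, the excess is between nothing and 1.9% at any interval the guideline itself uses, and it needs the compounded reading. With Table 1's lower stop at 180 sec, repeated steps mainly concern a patient who stays at about 180 to 200 sec. This stands for the first 30 minutes. It does not cover later titration.
- **Overshoot was the observed problem.** The Cohort 1 peaks are the reason both bolus and rate were lowered. This stands, and it is why a fourth step should be uncommon.
- **The MTD comparison is mild.** The MTD is a whole regimen and the top Phase 1 dose, with only Grade 1 treatment-emergent events and a mean peak ACT of 253.8 sec, inside the target range. The Cohort 3 bolus, even with top-up, stays below 1.2 mg/kg. This stands.
- **Adjustments are recorded.** Sections 8.2, 8.4 and 9.2.2 call for detailed records, so what each patient received can be recovered. That helps the analysis afterwards but does not define the rule in advance.

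A reader might infer from the permissive wording on extra ACT readings that sites may titrate blind. The documents do not support that: stepping until ACT exceeds 200 sec cannot be followed without a reading. What is missing is how often to take one. A reader might also infer that Cohort 3 patients will routinely pass the MTD rate, or that passing it has been shown to be harmful. The documents show neither.

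**Conclusion.** The point holds as a gap in the dosing rule. The text permits a rate above 2.3 mg/kg/h, at the fourth step if compounded or the fifth if additive, and no other provision caps it. That conclusion needs no assumption about timing. Placing the fourth compounded step at minute 25 assumes 5-minute steps; at 7 or 10 minutes the MTD rate is not reached before rescue. The best-supported excess before rescue is 0 to 1.9%. Any excess from later titration has no upper limit in the text and cannot be sized from the documents. With low expected frequency and limited known hazard, this is a minor point, but it is cheap to put right and it concerns patient safety.

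**What to change.** In section 8.2 and the synopsis:
- Cap the Cohort 3 infusion rate at 2.3 mg/kg/h, or at a lower value chosen by the Study Management Group.
- Define each step as 10% of the starting rate, 0.16 mg/kg/h, with at most four steps (2.24 mg/kg/h).
- Require an ACT reading before each step, at a stated minimum interval. Five minutes would match the guideline's own spacing.
- At the cap, hold the rate. Before PCI, the existing 30-minute rescue rule applies unchanged. During PCI, leave management to the investigator and the bail-out provisions of section 8.5.1, with no mandatory switch. That section requires 30 minutes off MT1002 before heparin or bivalirudin, so a forced switch could leave a patient without an anticoagulant in mid-procedure.
- Summarise delivered mg/kg per patient.

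With additive 5-minute steps the cap would not bind before rescue. There the defined step does the work, and the cap matters for later titration. A limit on cumulative dose can be left to the Study Management Group.

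The cost is a few sentences in two places and one summary row, from dose and time data that section 8.4 already sends to the eCRF. The downside is that a few low responders cannot be titrated further and may move to standard of care.

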8.3 Measures to Minimize Bias: Study Treatment Assignment

8.3.1 Method of Study Treatment Assignment

This is an open-label, sequential-dose escalation/de-escalation study testing 3 dose levels of MT1002. The decision on dose escalation/de-escalation/stopping or continuation for the patient cohort will be made by the Study Management Group based on data review of each dose group considering safety, efficacy, PK, and in conjunction with the prespecified criteria in Section 6.1.

8.3.2 Blinding

This is an open-label study; therefore, blinding is not applicable.

8.4 Treatment Accountability and Compliance

The pharmacist or other designated individual will be responsible for: maintaining records of study drug delivered to the study site, the inventory at the study site, the distribution to and use by each patient, and the return of materials to the Sponsor for storage or disposal. These records should include dates, quantities, batch/serial numbers, expiration dates, in-clinic temperature log, and unique code numbers assigned to the product and study patients.

The study drug will only be applied by the Investigator on Day 1 (prior, during, and after PCI). The timing and duration of the loading dose followed by infusion as well as the dose calculation depending on the patient's weight will be noted in the patient's medical file. Early termination of infusion and reason for termination will also be recorded in the eCRF.

Administration of study drug will be performed by study site personnel, and the date, time, and dose information will be recorded in the eCRF.

8.5 Prior and Concomitant Therapy

8.5.1 Prior and Concomitant Medications

Restricted prior therapies that exclude patients from the study are provided in Section 7.2.

All cardiovascular, antiplatelet, anticoagulant, and diabetic medications and other treatments taken by the patient during the study, including those treatments initiated or ongoing within 48 hours before the start of the study, must be recorded on the eCRF (based on patient/caregiver report and/or medical records).

Concomitant anticoagulant medications before enrollment:

Unfractionated heparin: UFH administered to patients before enrollment will be discontinued at the time of enrollment with MT1002 allocation (if not already discontinued). MT1002 can be administered after discontinuation of intravenous UFH or 4 hours after subcutaneous UFH discontinuation provided ACT is <200 seconds. The wash-out period for UFH should help to

ensure complete UFH elimination⁵ to avoid initial ACT increase due to residual heparin effect that could confound the analysis of MT1002's effect on the indices of coagulation.

Low molecular weight heparin: LMWH administered to patients before enrollment will be discontinued at the time of enrollment with MT1002 allocation (if not already discontinued). MT1002 can be administered 8 hours after subcutaneous low molecular weight heparin discontinuation provided ACT is <200 seconds.

Patients receiving fondaparinux for the index admission before enrollment with MT1002 allocation should not be included in the study.

Background therapy:

Acetylsalicylic acid: On admission, all patients will be administered a loading dose of aspirin approximately 325 mg (not exceeding 400 mg, if not already on a maintenance dose) and will stay on 75-100 mg/day (according to local countries clinical practice guidance) as maintenance therapy. Patients should continue aspirin for the remainder of the study period (i.e., through 30 days post-dose) or longer per local standard of care. This background medication will not be provided as part of the clinical trial supplies, unless required by local laws and regulations.

Clopidogrel: On admission, all patients will receive a loading dose of clopidogrel (600 mg) if not already on a maintenance dose, and then stay on a maintenance dose of 75 mg/day. Patients should continue this ADP/P2Y₁₂ inhibitor for the remainder of the study period (i.e., through 30 days post-dose) or longer per local standard of care, as outlined by the current ACCF/AHA and European Society of Cardiology Guidelines.

Ticagrelor or Prasugrel: if the local clinical guidance recommends use of Ticagrelor or Prasugrel, the recommended doses will be: On admission, all patients will receive a loading dose of Ticagrelor 180 mg if not already on a maintenance dose, and then stay on a maintenance dose of 90 mg twice daily. Or on admission, all patients will receive a loading dose of Prasugrel 60 mg if not already on a maintenance dose, and then stay on a maintenance dose of 5-10 mg daily. Patients should continue this ADP/P2Y₁₂ inhibitor for the remainder of the study period (i.e., through 30 days post-dose) or longer per local standard of care, as outlined by the current ACCF/AHA and European Society of Cardiology Guidelines.

In this study, clopidogrel (or Ticagrelor or Prasugrel) and acetylsalicylic acid are considered non-investigational medicinal products. This means that in the event of an SAE, the Investigator will assess the causal relationship of the SAE to the non-investigational medicinal product.

Bivalirudin: Patients receiving bivalirudin before enrollment into the study for the index MI should not be included in the study. Patients who fail to achieve the ACT target of 200 to 300 sec with MT1002 (within 30 minutes after MT1002 infusion initiation) can be switched to bivalirudin before PCI as a standard of care. Bivalirudin cannot be administered simultaneously with MT1002; MT1002 treatment should be discontinued at least 30 mins before switching to bivalirudin (dosing per local standard of care).

Glycoprotein IIb/IIIa inhibitors: Upstream use of glycoprotein IIb/IIIa inhibitors (i.e., within 24 hours before enrollment) is an exclusion criterion. After enrollment, glycoprotein IIb/IIIa inhibitors may be used as bail out for procedural or angiographic complications or clinical instability (dosing per local standard of care). Glycoprotein IIb/IIIa inhibitors cannot be administered simultaneously with MT1002; MT1002 treatment should be discontinued 30 minutes before switching to glycoprotein IIb/IIIa inhibitors.

Aspirin, clopidogrel (or Ticagrelor or Prasugrel), bivalirudin as a rescue therapy, and glycoprotein IIb/IIIa inhibitor as bail out for PCI is standard practice and not exclusive to this study. Therefore, these agents will be supplied by the hospital pharmacy or other local qualified pharmacy source as part of the local standard of care.

Concomitant anticoagulant therapy:

All patients should receive evidence-based medications for coronary artery disease (e.g., beta-blockers, ACE-inhibitors, statins, diabetic medications, etc.) as recommended in practice guidelines and/or per local standard of care. Concomitant medications through Day 30 will be recorded in the source documents and eCRF. In addition:

- Heparin is not permitted from enrollment through 7 hours post-MT1002 infusion completion except for the following situations (per local standard of care):
 - After enrollment, patients who fail to achieve ACT target of 200 to 300 sec with MT1002 (within 30 minutes after MT1002 infusion initiation) can be switched to UFH as a standard of care. UFH cannot be administered simultaneously with MT1002; MT1002 treatment should be discontinued 30 minutes before switching to UFH (dosing per local standard of care).
 - In the case of intracoronary or stent thrombosis during the procedure or within 24 hours after the procedure, heparin may be administered as a bail out therapy if it is deemed that inadequate anticoagulation has been achieved with MT1002 based on clinical or angiographic findings.
Monitoring of ACT levels and administration and dosing of UFH should be performed per local standard of care and should be continued to maintain a therapeutic level of anticoagulation.
 - In patients undergoing emergent or urgent open-heart surgery after the PCI
 - In patients undergoing urgent device placement that requires continuous anticoagulation (e.g., intra-aortic balloon pump)
 - For routine flushing of catheters and IV lines, including radial or femoral access catheters.
- Heparin is permitted after 4 hours post sheath removal (per local standard of care).

The concomitant administration of proton pump inhibitors is strongly recommended in patients without clinical contraindications for those agents, to reduce the risk of gastrointestinal bleeding. Proton pump inhibitors that do not interact with CYP2C19 (lansoprazole, pantoprazole, etc.) should be used.

The Investigator is responsible for ensuring that procedures and expertise are available to handle medical emergencies that may occur during the study.

Medications taken by or administered to the patient for the time period before Screening will be recorded in the eCRF. After the baseline visit, medication to treat minor treatment-emergent illness(es) is generally permitted.

Any medication or therapy that is taken by or administered to the patient during the course of the study must be recorded in the eCRF. The entry must include the dose, regimen, route, indication, and dates of use.

